Grade advancement or graduation rates

Additional data points to be obtained for subgroup analyses include:

- At the individual level:
 - Sex - male or female
 - Ethnicity - Hispanic vs. non-Hispanic
 - Race - white, black or other
 - Urban/rural – students will be categorized as enrolled in urban or rural school districts based on the definition applied by The Center for Rural PA, a Legislative Agency of the PA General Assembly for the district

- At the aggregate level, the following variables will be collected:
 - District socioeconomic status
 - School size – school enrollment. Data will be obtained from school districts based on enrollment as of October 1 of the RCT
 - Ratio of guidance counselors/students – The ratio of counselors to students will be obtained from each school district
 - School-based mental health services – schools will be categorized by the availability of school-based mental health services (yes vs. no) based on information obtained from each school district.

We need to collect data at the individual level for 3 main reasons. First, we expect approximately 20% of students to opt out from the study, with opt out rates varying by grade. Aggregate data would necessarily include outcomes for students who are not enrolled in the study. This is particularly problematic for the universal screening group because students who opt out will not be offered the depression screening tool (PHQ-9). Second, we need to obtain gender and race/ethnicity to conduct important planned secondary analyses (subgroup analyses) that will examine efficacy of universal screening by these groups. In particular, we expect that females and minority students will have much higher rates of major depression disorder identified in the universal screening group. Third, in the universal screening group, we will be able to link responses to the PHQ-9 to outcomes, which will allow for estimation of important measures such as the false positive rate of the PHQ-9 (score ≥ 11 , but SAP process determines no further referrals are needed). These measures will inform decision-making regarding the potential for implementation of the intervention (in other schools) should the results of the trial ultimately show efficacy.

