7.0 Study Design and Procedures

7.1 Study Design

Due to the timeline for this funding opportunity, with an anticipated July 2018 start, 3 schools will engage in the randomized control trial (RCT) in study year 1 and the additional 13 schools in study year 2. Many large scale randomized control trials do not enroll all participants at one time point, and in many cases enrollment occurs slowly over the course of several years. We do not anticipate there will be major changes over the course of two academic years that would significantly alter the results compared to conducting the RCT in the same academic year, especially because students will be randomized within schools. Finally, staggering enrollment will give the research team the opportunity to troubleshoot any unanticipated issues with the first 3 participating schools. The intervention ended early in study year 2 (March 2020) due to the COVID-19 pandemic and schools subsequently ending in-person instruction.

The study team was unable to complete PHQ-9 screeners with two participating schools [REDACTED]. SAP outcome data will still be collected for all enrolled students (i.e., those whose parents did not return the opt-out form) for the 2019-2020 (study year 2) school year. At the completion of the year one screener/ screening process, school staff will be asked to complete the Final Feedback Guide document to assist in our research/ knowledge of the study process and procedures. Staff members from two schools completed the Feedback Guide interview [REDACTED] as a pilot to ensure the final version of the Feedback Guide was thorough and comprehensive.

At the completion of the of the 2019/2020 school year, the 3 schools that participated in the RCT during the 2018/2019 school year, will be asked to complete the Year 2 feedback guide interview document to assist in our research/knowledge of the long-term feasibility and sustainability of study processes and procedures. During their second year of study participation, school participants will be asked to complete the feedback guide interview with research personnel. Due to the COVID-19 pandemic occurring during the 2019-2020 school year, we have added questions relevant to student mental health concerns.

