7.2.2 Randomization

We will randomize by grade levels within each school to receive either one-time universal screening (via PHQ-9) or targeted screening (current SAP process). For the schools included in the study, half of the schools (50%) will be randomized such that students in 9th and 11th grades will receive universal screening and students in 10th and 12th grades will receive targeted screening, and the other half (50%) will be randomized such that students in 9th and 11th grades will receive targeted screening and students in 10th and 12th grades will receive universal screening. Randomization will be done only for students whose parents do not signal an unwillingness to participate in the study (“opt out”). Students and study personnel will not be blinded to randomized group at each school site. Randomization will be done by grade level primarily for pragmatic reasons because many PA health-based screenings are grade-specific (e.g. hearing screen in 11th grade) and screenings for a grade occur at the same time. The study will be conducted within schools, but it is not a cluster randomized study, in which an entire school (cluster) is assigned to one of the study groups. A cluster randomized study was considered but ultimately not pursued because randomization within schools controls for (1) within-school (community) factors that may contribute to higher or lower rates of SAP referral, (2) differences in school sizes, and (3) potential differences in rates of parental opt out among schools. These benefits were balanced against the concern of potential contamination between study groups, whereby those in the targeted screening group may benefit from the school-wide push to conduct universal screening.

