8.3 Statistical methods

The principles of intention-to-treat (ITT) will be used for all statistical analyses related to primary and secondary aims. For the primary aim comparing universal to targeted screening, the statistical analysis will be conducted using a mixed effects logistic regression model. The primary outcome, MDD composite, will be an indicator whether a student was screen positive (or concerns raised in the targeted screening arm), identified as having MDD and subsequently engaged in treatment (1=yes, 0=no). The model will include a fixed effect for randomized group (0=targeted screening, 1=universal screening) and a random effect for school. The random effect accounts for correlation among students enrolled within the same school. The primary parameter of interest will be the log odds of MDD composite in the universal screening group compared to the targeted screening group. Statistical significance of the log odds will be assessed using a 2-sided Wald test. Point estimates for the odds ratio along with a 95% confidence interval will be reported.

For the analysis of Hypotheses 2 and 3 (Objective 1) evaluating universal screening and targeted screening by selected subgroups, the same mixed effects logistic regression modeling framework will be used, but the model will be extended by including a fixed effect for subgroup and an interaction effect for subgroup by randomized group. The interaction term will be the parameter of interest. A significant interaction term indicates that rates of MDD treatment engagement for universal versus targeted screening differ by subgroup level (e.g. female vs. male). For the secondary analyses (Objective 2) that evaluates universal screening and targeted screening based on school SAP data, we will have only 64 total data points (4 grades in each of the 14 schools). Mixed-effects linear (continuous outcomes) and logistic regression (binary outcomes) will be used, as appropriate, with a fixed effect for randomized group and a random effect for school. The parameter of interest will be the log odds for the universal compared to the targeted screening group. Due to the smaller sample size used for these outcomes, these analyses will be considered to be primarily hypothesis-generating. Potential mediating variables (socioeconomic status, ratio of guidance counselors to students and availability of school-based mental health services) will be evaluated for both the Objective 1 and 2 hypotheses.

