Additional secondary outcomes will include MDD screen results, MDD concern prompting Student Assistance Program triage, MDD identification and MDD treatment engagement analyzed individually (rather than as part of MDD composite). Finally any suicidal adolescents (suicidal thoughts [positive response to PHQ-9 item 9], attempts and completed) will be analyzed as a secondary outcome.

We need to collect data for individuals for 3 main reasons. First, we expect approximately 20% of students to opt out from the study, with opt out rates varying by grade. Aggregate data would necessarily include outcomes for students who are not enrolled in the study. This is particularly problematic for the universal screening group because students who opt out will not be offered the depression screening tool (PHQ-9). Second, we need to obtain gender and race/ethnicity to conduct important planned secondary analyses (subgroup analyses) that will examine efficacy of universal screening by these groups. In particular, we expect that females and minority students will have much higher rates of major depression disorder identified in the universal screening group. Third, in the

universal screening group, we will be able to link responses to the PHQ-9 to outcomes, which will allow for estimation of important measures such as the false positive rate of the PHQ-9 (score ≥ 11 , but SAP process determines no further referrals are needed). These measures will inform decision-making regarding the potential for implementation of the intervention (in other schools) should the results of the trial ultimately show efficacy.

Efforts will be made to ensure completeness of data where possible, but missing data will occur for a number of anticipated reasons. First, a student may move during the course of the school year to another school district or drop out from school entirely. No data will be collected after this time point. Second, parents may opt out their child from the study at any time during the school year. Third, students who turn 18 during the school may decide to opt out of the study themselves. In both of these instances, data from SAP referrals that occur after opting out will not be collected for purposes of the study. Fourth, during the one-time universal screening phase, students may decide to leave data forms incomplete, including the PHQ-9. To decrease these instances, the PHQ-9 will be taken on an iPad program and the survey will alert if the form is left incomplete.

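### The Objective 2 models omit grade although arm is assigned by grade pair, name a log odds for linear models, and count 64 rows where 4 x 14 gives 56

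*Combined protocol and SAP*

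**What the plan says.** All references are to the current protocol, the later of the two in the combined document.

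- **Allocation (7.2.2).** In half of the schools, "students in 9th and 11th grades will receive universal screening and students in 10th and 12th grades will receive targeted screening"; the other half have the mirror pattern.
- **Data (1.1, Objective 2).** The outcomes come as aggregates by grade level at each school, so a row is one grade in one school.
- **Model (8.3).** Continuous outcomes get a mixed-effects linear model. For binary outcomes, "logistic regression (binary outcomes) will be used, as appropriate, with a fixed effect for randomized group and a random effect for school". Grade is neither a model term nor among the potential mediators listed.
- **Effect measure (8.3).** For both kinds of model, "The parameter of interest will be the log odds for the universal compared to the targeted screening group".
- **Rows (8.3).** The text states that "we will have only 64 total data points (4 grades in each of the 14 schools", and 1.1 repeats the count. Section 7.1, however, says that "3 schools will engage in the randomized control trial (RCT) in study year 1 and the additional 13 schools in study year 2".
- **Status (8.3).** "Due to the smaller sample size used for these outcomes, these analyses will be considered to be primarily hypothesis-generating". Section 1.1 adds that these outcomes may be unavailable after the COVID-19 closures.

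**The concern.** Grade defines both the unit of analysis and the allocation, but the model does not contain it. The outcomes listed in 1.3 make grade differences plausible: "Grade advancement or graduation rates" is a different quantity in grade 12 than in grades 9 to 11.

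In a linear model without grade, such differences go into the residual. The interval is then wider than the data warrant and the test is conservative. With so few rows, that weakens an analysis whose purpose is to find signals.

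Two wording faults sit in the same paragraph. A linear model yields a mean difference, not a log odds. And the row count does not follow from the school count beside it.

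**Working it through.** **1. Row count.** Rows = grades x schools.

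- 14 schools (1.1, 3.1, 8.3): 4 x 14 = 56. The stated 64 is not reproduced.
- 3 + 13 = 16 schools (7.1): 4 x 16 = 64. This reproduces the figure, but with a different school count.
- The superseded protocol in the same file was consistent: 4 x 8 = 32.

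**2. Linear model, equal split (7:7, 56 rows).** The unit is the residual SD, that is, cell-to-cell SD after school and grade. Every school has two grades in each arm, so the arm estimate is a within-school contrast with standard error sqrt(4/56) = 0.267. Every grade has 7 cells in each arm, so arm is orthogonal to grade and the estimate is the same with or without grade.

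Residual degrees of freedom:
- without grade: 56 - 14 - 1 = 41
- with grade: 41 - 3 = 38

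Half-width with grade: t(38) x 0.267 = 2.024 x 0.267 = 0.541.

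Without grade, the grade sum of squares (expected value 14 x 3 x g² beyond noise, where g is the grade SD) enters the residual. The expected residual variance becomes 1 + (42/41)g², and the half-width is about 2.020 x 0.267 x sqrt(1 + (42/41)g²). The documents give no value for g, so it is assumed over a range:

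| g (assumed) | Formula, no grade | Simulated mean, no grade | Simulated mean, with grade | Coverage, no grade |
|---|---|---|---|---|
| 0 | 0.540 | 0.54 | 0.54 | 95% |
| 0.5 | 0.605 | 0.60 | 0.54 | about 97% |
| 1 | 0.768 | 0.75 | 0.54 | about 98.6% |

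The simulation used 20,000 data sets per row, school SD 1 and a true arm effect of 0. School was fitted as indicators, which stand in closely for the planned random effect over this range. The simulated means lie slightly below the formula because the mean of a square root is less than the root of the mean. The true SD of the estimate is 0.27 in every row, so the extra width is not real uncertainty.

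**3. Linear model, unequal split.** Each 9/11-universal school adds the gap between the 9/11 and 10/12 means to its arm contrast; each mirror school subtracts it. Without grade:

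shift = (8 - 6)/14 x gap = 1/7 x gap = 0.143 x gap at 8:6.

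For an assumed trend of 0.5 SD per grade the gap is 0.5 SD in size and the shift 0.07 SD. For 1 SD per grade it is 0.14 SD. Simulation gives the same values, and no shift once grade is in the model. The with-grade half-width at 8:6 is 0.54 (0.543 simulated).

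**4. Binary outcomes as grouped counts.** Here the problem differs. Assumptions: 172 students per cell (9,640/56), a 10% base rate, school SD 0.4 and steps of 0.2 per grade on the logit scale, and extra cell-to-cell SD s on that scale. Type I error at 7:7, nominal 0.05, 500 runs per row (simulation error about 0.01 at 0.05, about 0.02 at 0.2):

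| s (assumed) | No grade | Grade | Grade + overdispersion scaling |
|---|---|---|---|
| 0 | 0.058 | 0.054 | 0.036 |
| 0.2 | 0.156 | 0.156 | 0.068 |
| 0.3 | 0.230 | 0.228 | 0.048 |

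A rough check is variance inflation of about 1 + m p(1 - p)s². At s = 0.2 this is 1 + 172 x 0.09 x 0.04 = 1.62, which implies an error of about 0.12. At s = 0.3 it is 2.39, which implies about 0.21. These are the same order as the simulated values. Grade alone does not calibrate these models; an overdispersion term does.

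**The case against.** The strongest reply is that the design already does most of the work. The mirror allocation balances grade across arms, so the linear estimate is unbiased under an equal split. What remains is a conservative interval in secondary analyses that the plan calls hypothesis-generating and that may not be run at all. The size of the loss rests on assumed grade differences and is nil if grades do not differ. The log odds and the 64 are editing slips that no statistician would carry into the analysis. All of this is fair, and it sets the weight of the point. It does not remove it: grade already indexes every row, and leaving it out gains almost nothing.

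Four stronger readings are tempting but not supported.

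- **That the arm effect is confounded with grade.** Section 7.2.2 prescribes equal halves with opposite patterns.
- **That departures of schools have unbalanced the split.** The Summary of Changes logs removals, but names are redacted and no realised split is given. An 8:6 split is an illustration. If it occurred through random departures, it would be chance imbalance, not a systematic bias of the randomization.
- **That opt-out "with opt out rates varying by grade" shows that these outcomes differ by grade.** The same part of 8.3 says that aggregate data include students who are not enrolled, so opt-out does not determine who is in the whole-grade figures.
- **That every interval is too wide and a grade term repairs it.** That account holds for the linear models only. With extra cell-to-cell variation, the grouped binary models err the other way, with or without grade.

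**Conclusion.** The point holds as a low-stakes improvement to the Objective 2 analyses. The textual parts are certain: there is no grade term, a log odds is named for linear models, and 64 is not 4 x 14.

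The cost of omitting grade from the linear models depends on grade differences that the documents do not give. It is nothing at a grade SD of 0, about 11% extra width at 0.5 residual SD (0.60/0.54), and about 39% at 1 (0.75/0.54). A shift of the estimate arises only if the pattern split is unequal. The type I error figures for binary outcomes rest on the assumed base rate and cell-to-cell SD.

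The documents do not settle whether 14 or 16 schools are analysed, so 56 cannot simply replace 64. The primary analysis uses individual data, not these rows, and this point does not bear on it.

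**What to change.** In 8.3, with matching edits in 1.1 and 7.1:

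1. Add grade (9 to 12) as a fixed effect in all Objective 2 models.
2. Report a mean difference for continuous outcomes and an odds ratio for binary ones.
3. For every binary outcome fitted as grouped counts (suspensions, grade advancement or graduation), also allow for overdispersion, for example with a random effect for grade within school.
4. Reconcile the number of schools across 1.1, 7.1 and 8.3, and set the data points to 4 x the schools analysed: 56 for 14, 64 for 16.

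The cost is wording and three degrees of freedom (41 to 38 with 56 rows). If grade does not matter, the half-width stays at 0.54 SD at a 7:7 split and rises by less than 0.01 SD at 8:6 (0.536 to 0.543). No new data are needed.

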9.0 Confidentiality, Privacy and Data Management

Please see HRP-598 - Research Data Plan Review Form

10.0 Data and Safety Monitoring Plan

N/A: This study does not involve more than minimal risk to subjects, and the magnitude of harm/discomfort is not greater than that ordinarily encountered in daily life.

11.0 Risks

Risk involved in participating in this study are low aside from identification of a suicidal student, in which case measures are already currently in place in each school building to address.

12.0 Potential Benefits to Subjects and Others

12.1 Potential Benefits to Subjects

Potential benefit to subjects of positive screenings include a referral to SAP to receive support in managing their MDD.

12.2 Potential Benefits to Others

The potential public health impact of the proposed project cannot be overstated. MDD is a prevalent, disabling and a growing US public health problem. The problem is identified by national organizations focused on our country's health care priorities (Healthy People 2020, US Department of Health and Human Services). MDD leads both to functional impairment and higher rates of morbidity and mortality. In addition, MDD leads to significant social and economic consequences, including increased use of health resources and lost work productivity. A public health goal should include identification of those at risk for depression with the delivery of interventions to these individuals. Schools are a point of intervention with a high potential for early identification and prevention. Currently, fewer than 2 out of every 100 adolescents receives guideline-concordant major depression screening. We propose reaching nearly 80 of every 100 adolescents in the school setting, vastly increasing the identification of adolescents suffering from MDD with a goal to decrease both morbidity and mortality. Schools are an ideal partner for this approach, given their tremendous reach across the nation to nearly all adolescents.

13.0 Sharing Results with Subjects

Individual results will not be shared with other participants.

14.0 Subject Stipend (Compensation) and/or Travel Reimbursements

N/A

15.0 Economic Burden to Subjects

15.1 Costs

There are no financial costs associated with participating in this research.

15.2 Compensation for research-related injury

N/A

16.0 Resources Available

16.1 Facilities and locations

Screening will take place in each of the 4 school buildings previously identified for the 2018-2019 school year. The study team will submit a finalized list of schools in advance of the 2019-2020 screenings.

16.2 Feasibility of recruiting the required number of subjects

All 4 school districts for the 2018-19 year have already expressed interest in participating as evidenced through letters of support. Current relationships through past and present programming with the school districts created feasibility for recruitment.

16.3 PI Time devoted to conducting the research

██████████ will monitor the progress of the study during all phases and hold bi-weekly meetings with research staff.

16.4 Availability of medical or psychological resources

It is not anticipated that medical or psychological resources will be needed on site, given that study procedures are minimal risk. However, students with suicidal intent will receive immediate evaluation and referral to emergency care as per current school protocols. PA schools are required to have a plan to address suicidal students. A QPR trained staff member will be available at the time of screening. Students with a PHQ-9 score ≥ 11 will proceed to Student Assistance Program triage as per the standard of care by which students exhibiting concerning behavior (outbursts, declining grades) would be referred for assessment.

